No dose adjustment is necessary when co-administering ruxolitinib with strong CYP3A4 inducers. No dose adjustment is necessary when co-administering ruxolitinib with CYP3A4 substrates. Ruxolitinib did not decrease the exposure of a fixed dose oral contraceptive metabolized via the CYP3A4 pathway, thus demonstrating lack of CYP3A4 induction potential.

In patients with severe (creatinine clearance (Cl_{cr}) <30 mL/min) and moderate renal impairment (Cl_{cr} = 30-59 mL/min), the recommended starting dose based on platelet count should be reduced by approximately 50% to be administered twice a day. Patients on hemodialysis should initiate ruxolitinib with a single dose of 15 mg or 20 mg based on platelet counts on day of hemodialysis with subsequent doses only on hemodialysis days and following each hemodialysis session. Ruxolitinib doses should be titrated based on individual safety and efficacy.

In patients with mild, moderate or severe hepatic impairment, the recommended starting dose based on platelet count should be reduced by approximately 50% with subsequent dose titration based on individual safety and efficacy.

Ruxolitinib PK in healthy volunteers was largely comparable between Japanese, Chinese and Western subjects and did not lead to a conclusion of meaningful ethnic differences.

Baseline elevations in inflammatory markers such as tumor necrosis factor alpha (TNF α), interleukin (IL)-6, and C-reactive protein (CRP) noted in patients with MF were associated with constitutional symptoms such as fatigue, pruritus, and night sweats. Decreases were observed in these markers over the 24 weeks of treatment with ruxolitinib, with no evidence that patients became refractory to the effects of ruxolitinib treatment.

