2.2 Rationale for the study design

The COMFORT studies compared the effects of ruxolitinib with placebo or best available therapy, respectively and showed that ruxolitinib treatment significantly reduced splenomegaly and provided marked improvements in MF-related symptoms and quality-of-life (QOL) measures compared with controls, regardless of JAK2V617F mutational status. The clinical benefit and safety of ruxolitinib treatment in COMFORT -I and COMFORT-II have been maintained with subsequent longer-term follow-up. As anticipated, the effect of JAK2 inhibition on hematopoiesis resulted in dose-dependent anemia and thrombocytopenia. The majority of these cytopenias occurred in the first 8 to 12 weeks of treatment, and they were generally manageable with dose reductions and/or red blood cell transfusions.

There is increasing literature suggesting the use of a 10 mg BID starting dose with subsequent up titrations depending on safety and efficacy in patients with anemia at the time of treatment initiation with ruxolitinib (Tabarrokhi 2013, Cervantes 2014, Reilly 2014, Harrison 2013, Ho 2015). This dosing approach for anemic MF patients will be systematically studied in this prospective multicenter phase II open label single arm trial to determine if the levels of spleen length reduction and symptom improvement are consistent with those reported in previous clinical trials with ruxolitinib in patients with anemia and doses according to platelet counts at the moment of treatment initiation, and whether this lower starting dose and up titration approach may minimize the initial hemoglobin and platelet declines and transfusion requirements. The efficacy and safety of ruxolitinib with starting doses based on platelet counts in MF patients including those with anemia at baseline have been well studied and characterized in several clinical trials (COMFORT I, COMFORT II, JUMP).

This is an open-label, single-arm study of treatment with ruxolitinib for 48 weeks in patients who presents with transfusion dependent or independent anemia at screening defined as an hemoglobin <10 g/dL.

Ruxolitinib will be self-administered as BID oral treatment. The starting dose is 10 mg BID for all enrolled patients and gradual up titrations will start at week 12 determined by the level of efficacy achieved and the tolerability.

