5.3 Exclusion criteria

Patients eligible for this study must not meet **any** of the following criteria:

1. Patients with prior treatment with any JAK1 or JAK2 inhibitor.
2. Patients with known hypersensitivity to ruxolitinib or other JAK1/JAK2 inhibitors, or to their excipients.
3. Patients eligible for hematopoietic stem cell transplantation (suitable candidate and a suitable donor is available).
4. Patients with inadequate bone marrow reserve at baseline as demonstrated by at least one of the following:
 - a. ANC that is $\leq 1,000/\mu\text{L}$.
 - b. Platelet count that is $< 50,000/\mu\text{L}$ without the assistance of growth factors, thrombopoietic factors or platelet transfusions.
 - c. Hemoglobin count that is ≤ 6.5 g/dL despite transfusions.
5. Patients with severely impaired renal function defined by:
Creatinine clearance less than 30 mL/min.
6. Patients with inadequate liver function defined by any of these:
 - a. Total bilirubin ≥ 2.5 x ULN and subsequent determination of direct bilirubin ≥ 2.5 x ULN;
 - b. Alanine aminotransferase (ALT) > 2.5 x ULN;
 - c. Aspartate aminotransferase (AST) > 2.5 x ULN.
7. Patients being treated concurrently with a strong (potent) systemic inhibitor or inducer of CYP3A4 at the time of Screening.
8. Presence of active bacterial, fungal, parasitic, or viral infection which requires therapy.
9. Known history of human immunodeficiency virus (HIV) infection or other immunodeficiency syndromes such as X-linked agammaglobulinemia and common variable immune deficiency.

10. Acute viral hepatitis or active chronic hepatitis B or C infection. Patients with *inactive* chronic infection (without viral replication) can be enrolled (See [Section 7.2.2.7](#))
11. History of progressive multifocal leuko-encephalopathy (PML).
12. Impairment of gastrointestinal (GI) function or GI disease that may significantly alter the absorption of ruxolitinib (e.g., ulcerative diseases, uncontrolled nausea, vomiting, diarrhea, malabsorption syndrome, small bowel resection).
13. History or current diagnosis of uncontrolled or significant cardiac disease, including any of the following:
 - a. Myocardial infarction within last 6 months
 - b. Uncontrolled congestive heart failure
 - c. Unstable angina within last 6 months
 - d. Clinically significant (symptomatic) cardiac arrhythmias (e.g. bradyarrhythmias, sustained ventricular tachycardia, and clinically significant second or third degree AV block without a pacemaker)

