6.3.1.3 Dose modification for hepatic impairment

Patients diagnosed with hepatic impairment while receiving ruxolitinib should be carefully monitored and may need to have their dose reduced to avoid adverse drug reactions.

Patients diagnosed with hepatic impairment while receiving ruxolitinib should have complete blood counts, including a white blood cell count differential (neutrophils, lymphocytes, eosinophils, basophils, monocytes, and blast cells), monitored at least every one to two weeks for the first 6 weeks after initiation of therapy with ruxolitinib and as clinically indicated thereafter once their liver function and blood counts have been stabilized. ruxolitinib dose can be titrated to reduce the risk of cytopenia.

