6.4.2 Permitted concomitant therapy requiring caution and/or action

The following medications have restrictions on use, dose, or require changes to the way in which ruxolitinib is administered during the study:

- In patients for whom warfarin or heparin use will be initiated, the degree of thrombocytopenia should be considered, coagulation parameters monitored, and dose of anticoagulant adjusted accordingly. If anticoagulation is required during ruxolitinib administration, low molecular weight heparin is preferred, particularly in patients who are: elderly, history of CHF, diabetic, hepatic or renal disease, or atrial fibrillation (first episode).
- Low dose aspirin (≤ 150 mg/day) and non-steroidal anti-inflammatory agents (acetaminophen, ibuprofen) may be used. Aspirin doses > 150 mg are prohibited.
- Inducers or inhibitors of the metabolizing enzyme CYP3A4 (Appendix 5)
- When concomitant administration of a strong (potent) inhibitor of CYP3A4 metabolizing enzymes or dual CYP2C9/CYP3A4 inhibitors (Appendix 5) is required for patient management, the dose of ruxolitinib tablets must be reduced by approximately 50% to be administered twice daily by decreasing the twice daily dose or by decreasing the frequency of dosing to the corresponding once daily dose when twice daily dose is not practical.
 - Note: No dose adjustment of ruxolitinib is needed for use with topical ketoconazole.

- Note: More frequent monitoring of hematology parameters and clinical signs and symptoms of ruxolitinib related adverse reactions is recommended upon initiation of a strong (potent) CYP3A4 inhibitor.
- No dose adjustment will be made when moderate systemic CYP3A4 inducers ([Appendix 5](#)) are co-administered with study treatment.
- Granulocyte growth factors are not allowed while study treatment is being administered but may be used for severe neutropenia at the Investigator's discretion while study medication is being withheld.
- Certain herbal supplements see [Appendix 5](#) are prohibited. Because the composition, pharmacokinetics and metabolism of many herbal supplements are unknown, the concurrent use of all herbal supplements is strongly discouraged during the study however if used during the trial please ensure the treatment is entered on the proper eCRF page (see [Section 6.4.1](#)).

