Hepatic impairment

[figure not shown]
In patients with any hepatic impairment the recommended starting dose based on platelet count should be reduced by approximately 50% to be administered twice daily. Subsequent doses should be adjusted based on careful monitoring of safety and efficacy. Patients diagnosed with hepatic impairment while receiving Jakavi should have complete blood counts, including a white blood cell count differential, monitored at least every one to two weeks for the first 6 weeks after initiation of therapy with Jakavi and as clinically indicated thereafter once their liver function and blood counts have been stabilised. Jakavi dose can be titrated to reduce the risk of cytopenia.

Older people (≥65 years)

No additional dose adjustments are recommended for older people.

Paediatric population

The safety and efficacy of Jakavi in children aged up to 18 years have not been established. No data are available (see section 5.1).

Treatment discontinuation

Treatment may be continued as long as the benefit-risk remains positive. However the treatment should be discontinued after 6 months if there has been no reduction in spleen size or improvement in symptoms since initiation of therapy.

It is recommended that, for patients who have demonstrated some degree of clinical improvement, ruxolitinib therapy be discontinued if they sustain an increase in their spleen length of 40% compared with baseline size (roughly equivalent to a 25% increase in spleen volume) and no longer have tangible improvement in disease-related symptoms.

Method of administration

Jakavi is to be taken orally, with or without food.

If a dose is missed, the patient should not take an additional dose, but should take the next usual prescribed dose.

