Non-melanoma skin cancers (NMSCs), including basal cell, squamous cell, and Merkel cell carcinoma, have been reported in patients treated with ruxolitinib. Most of these patients had histories of extended treatment with hydroxyurea and prior NMSC or pre-malignant skin lesions. A causal relationship to ruxolitinib has not been established. Periodic skin examination is recommended for patients who are at increased risk for skin cancer.

Special populations

Renal impairment

The starting dose of Jakavi should be reduced in patients with severe renal impairment. For patients with end-stage renal disease on haemodialysis the starting dose for MF patients should be based on platelet counts (see section 4.2). Subsequent doses (single dose of 20 mg

or two doses of 10 mg given 12 hours apart in MF patients; single dose of 10 mg or two doses of 5 mg given 12 hours apart in PV patients) should be administered only on haemodialysis days following each dialysis session. Additional dose modifications should be made with careful monitoring of safety and efficacy (see sections 4.2 and 5.2).

Hepatic impairment

The starting dose of Jakavi should be reduced by approximately 50% in patients with hepatic impairment. Further dose modifications should be based on the safety and efficacy of the medicinal product (see sections 4.2 and 5.2).

Interactions

If Jakavi is to be co-administered with strong CYP3A4 inhibitors or dual inhibitors of CYP3A4 and CYP2C9 enzymes (e.g. fluconazole), the unit dose of Jakavi should be reduced by approximately 50%, to be administered twice daily (for monitoring frequency see sections 4.2 and 4.5).

The concomitant use of cytoreductive therapies or haematopoietic growth factors with Jakavi has not been studied. The safety and efficacy of these co-administrations are not known (see section 4.5).

Withdrawal effects

Following interruption or discontinuation of Jakavi, symptoms of MF may return over a period of approximately one week. There have been cases of patients discontinuing Jakavi who sustained more severe events, particularly in the presence of acute intercurrent illness. It has not been established whether abrupt discontinuation of Jakavi contributed to these events. Unless abrupt discontinuation is required, gradual tapering of the dose of Jakavi may be considered, although the utility of the tapering is unproven.

Excipients

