Dose proportionality was demonstrated in the single and multiple dose studies.

Special populations

Effects of age, gender or race

Based on studies in healthy subjects, no relevant differences in ruxolitinib pharmacokinetics were observed with regard to gender and race. In a population pharmacokinetic evaluation in MF patients, no relationship was apparent between oral clearance and patient age or race. The predicted oral clearance was 17.7 l/h in women and 22.1 l/h in men, with 39% inter-subject variability in MF patients. Clearance was 12.7 l/h in PV patients, with a 42% inter-subject variability and no relationship was apparent between oral clearance and gender, patient age or race, based on a population pharmacokinetic evaluation in PV patients.

Paediatric population

The safety and effectiveness of Jakavi in paediatric patients have not been established (see section 5.1, "Paediatric population").

Renal impairment

Renal function was determined using both Modification of Diet in Renal Disease (MDRD) and urinary creatinine. Following a single ruxolitinib dose of 25 mg, the exposure of ruxolitinib was similar in subjects with various degrees of renal impairment and in those with

normal renal function. However, plasma AUC values of ruxolitinib metabolites tended to increase with increasing severity of renal impairment, and were most markedly increased in the subjects with severe renal impairment. It is unknown whether the increased metabolite exposure is of safety concern. A dose modification is recommended in patients with severe renal impairment and end-stage renal disease (see section 4.2). Dosing only on dialysis days reduces the metabolite exposure, but also the pharmacodynamic effect, especially on the days between dialysis.

Hepatic impairment

Following a single ruxolitinib dose of 25 mg in patients with varying degrees of hepatic impairment, the mean AUC for ruxolitinib was increased in patients with mild, moderate and severe hepatic impairment by 87%, 28% and 65%, respectively, compared to patients with normal hepatic function. There was no clear relationship between AUC and the degree of hepatic impairment based on Child-Pugh scores. The terminal elimination half-life was prolonged in patients with hepatic impairment compared to healthy controls (4.1-5.0 hours versus 2.8 hours). A dose reduction of approximately 50% is recommended for patients with hepatic impairment (see section 4.2).

[figure not shown]

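### At platelet counts of 200,000/µL or below, the flat 10 mg BID start exceeds the halved starting dose that the protocol's background and appended label call for in hepatic impairment, and no treatment section covers impairment present at entry

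*Protocol*

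**What the plan says.** **Reduction rule.** Protocol 1.2.1.2.1: "In patients with mild, moderate or severe hepatic impairment, the recommended starting dose based on platelet count should be reduced by approximately 50" per cent. Appendix 6 (the label), section 4.2: "In patients with any hepatic impairment the recommended starting dose based on platelet count should be reduced by approximately 50" per cent. Section 4.4 of the label repeats it more shortly: "The starting dose of Jakavi should be reduced by approximately 50% in patients with hepatic impairment". In Protocol 1.2.1.2.1 and label 4.2, the dose to be reduced is the one set by platelet count.

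**Trial dose.** Protocol 2.2: "The starting dose is 10 mg BID for all enrolled patients". Section 6.1.1 keeps that dose for 12 weeks unless a hold or reduction criterion is met. It makes no provision for liver function at baseline.

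**Entry.** Criterion 6 of Protocol 5.3 has three limits: "Alanine aminotransferase (ALT) > 2.5 x ULN", the same limit for AST, and total bilirubin at or above 2.5 x ULN with direct bilirubin then also at or above 2.5 x ULN. There is no exclusion by Child-Pugh class, cirrhosis or hepatic impairment as such. Criterion 10 admits inactive chronic hepatitis B or C. Criterion 4b admits platelet counts from 50,000/µL.

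**On treatment.** Section 6.3.1.3 is the only hepatic dosing rule in the treatment section: "Patients diagnosed with hepatic impairment while receiving ruxolitinib should be carefully monitored and may need to have their dose reduced".

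**Exposure.** Label section 5.2 reports that after a single 25 mg dose "the mean AUC for ruxolitinib was increased in patients with mild, moderate and severe hepatic impairment by 87%, 28% and 65" per cent respectively. It adds that AUC showed no clear relationship with Child-Pugh score.

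**The concern.** Two parts of the protocol package say that the starting dose should be lower in hepatic impairment. The treatment section gives one dose to everyone and addresses the liver only after treatment has begun. A patient who is impaired at entry but passes criterion 6 therefore falls under a stated rule (10 mg BID for all) that can conflict with the background section and the label. An investigator who acted on section 1.2.1.2.1 would depart from section 6.1.1, and section 12 permits no authorized deviations, although sections 6.3.3 and 12.1 preserve action for patient safety.

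The stake is mainly safety in patients with low platelet counts. There is also a smaller interpretive cost. Section 2.3 assumes that a lower starting dose eases the early hemoglobin decline, and raised exposure in the first 12 weeks would work against that in any affected patient.

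**Working it through.** **1. The plan's own figures.** The design figures for 50 patients and at least 13 responders reproduce. The probability of success is 0.0301 at a true rate of 15% and 0.9339 at 35%, and the posterior probability of a rate at or below 15% with 13 of 50 is 0.0243 under the Beta(1/3, 1) prior. None of them depends on this point. What follows is a consistency check between sections.

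**2. Flat dose against halved label dose.** Inputs: the starting doses in label section 4.2 (20 mg BID above 200,000/mm³; 15 mg BID at 100,000-200,000; a maximum of 5 mg BID at 50,000 to <100,000), the approximate 50% reduction, and the trial's 10 mg BID. Ratio = 10 / (label dose / 2).

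| Platelets per µL | Label start | Halved | Trial dose / halved dose |
|---|---|---|---|
| >200,000 | 20 mg BID | 10 mg | 10 / 10 = 1.0 |
| 100,000-200,000 | 15 mg BID | 7.5 mg | 10 / 7.5 = 1.33 |
| 50,000 to <100,000 | 5 mg BID (maximum) | 2.5 mg | 10 / 2.5 = 4.0 |

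In the lowest band the factor of 4 splits into 10 / 5 = 2 from the trial's own departure from the label maximum and a further 2 from the hepatic halving.

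**3. Exposure.** Inputs: the AUC increases in label 5.2 and the dose proportionality stated in Protocol 1.2.1.2.1 and label 5.2. Equivalent dose in normal liver function = 10 mg x (1 + increase).

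- Mild: 10 x 1.87 = 18.7 mg BID
- Moderate: 10 x 1.28 = 12.8 mg BID
- Severe: 10 x 1.65 = 16.5 mg BID

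**4. Against the protocol's cited limits.** Sections 2.3 and 6.2.1 cite, from an ongoing phase Ib study, maximum safe starting doses of 10 mg BID at 50,000-75,000/µL and 15 mg BID at 75,000-100,000/µL.

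- At 50,000-75,000, all three equivalents exceed 10 mg.
- At 75,000-100,000, 12.8 mg lies below 15 mg; 16.5 and 18.7 mg lie above it.
- At 100,000-200,000, the same three values fall on either side of the label's unreduced 15 mg.
- Above 200,000, all three are below the label's unreduced 20 mg.

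**5. Can such patients enter?** ALT or AST up to 2.5 x ULN passes criterion 6. So does a raised total bilirubin with direct bilirubin below 2.5 x ULN, and so does impairment without enzymes or bilirubin beyond the limits. The documents neither define mild impairment nor link these limits to Child-Pugh class, so entry is an inference, though a reasonable one.

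**The case against.** The strongest reply is that the reduction applies to a platelet-based dose that this trial does not use, and that 10 mg BID is already a reduced dose. This stands in full above 200,000/µL and in part at 100,000-200,000, where the gap is 10 against 7.5 mg under a rule worded as approximate. At 50,000 to <100,000 half of the ratio comes from the trial's reasoned choice to start above the label maximum. What remains is that the protocol justifies 10 mg by anemia and nowhere says that it also allows for liver function.

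The second reply is that safeguards exist: the investigator-judged exclusion in criterion 14, the sponsor's eligibility check (7.1.2.1), chemistry and hematology at every visit (Table 7-1), mandatory count-based reductions (Table 6-2), and freedom to hold the drug (6.3.3). These limit the consequence. None says how to start a patient known to be impaired.

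A reader might infer two stronger things that the documents do not support:

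- *That mildly impaired patients would have nearly double the intended exposure.* The 87% is the highest of three means that do not rise with severity, from a single-dose study with no clear relation to Child-Pugh score. It cannot be assigned to everyone who merely passes criterion 6.
- *That the protocol is inconsistent with its own rule for strong CYP3A4 inhibitors, where* "the dose of ruxolitinib tablets must be reduced by approximately 50" *per cent.* Criterion 7 excludes those drugs at screening, and the reduction applies when one becomes necessary later. The liver follows the same pattern of an entry exclusion plus an on-treatment rule. The inhibitor rule is firmer in wording, but it is not an entry rule.

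**Conclusion.** The inconsistency is real but confined to patients with hepatic impairment at entry and platelets at or below 200,000/µL. There the trial dose is 1.33 times (100,000-200,000) or 4 times (50,000 to <100,000) the halved label dose. It is clearest at 50,000-75,000/µL, where any of the reported AUC increases would take exposure above the maximum safe starting dose that the protocol itself cites.

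The exposure range of roughly 12.8-18.7 mg BID assumes dose proportionality, that single-dose means carry over to twice-daily dosing, and that the cited maximum safe doses refer to patients without raised hepatic exposure, which the documents do not state. It is indicative only. The number of patients affected cannot be derived.

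It would be wrong to infer that all enrolled patients with impairment are affected, or that the primary result is compromised. The sample size and success rule do not change, and no effect on the response rate can be quantified from the documents.

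**What to change.** Reconcile Protocol 1.2.1.2.1, 5.3 (criterion 6), 6.1.1 and 6.3.1.3 with Appendix 6 section 4.2, for patients who have hepatic impairment at entry and platelets at or below 200,000/µL. The text should make clear what counts as hepatic impairment for this purpose and which section governs. Whether this is settled through eligibility or dosing is for the sponsor's clinical team; no dose or rule is proposed here.

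The cost is protocol wording or an amendment. No analysis, sample size or success criterion has to change.
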